7.6.5. Body Weight and Vital Signs

The observed value and percentage of changes from baseline will be summarized and listed by visit for Safety Analysis Set. If there are multiple measurements per visit, these measurements will be averaged.

Maximum weight loss from baseline will be summarized as 5 to <10% loss from baseline; 10 – <20% loss from baseline; and $\geq 20\%$ loss from baseline.

7.6.6. 12-lead Electrocardiogram

Number of subjects with abnormal clinically not significant and abnormal clinically significant electrocardiogram (ECG) results, as well as number of subjects with QTc_F (QT interval corrected using Fridericia’s formula) greater than 450, 480, or 500 milliseconds will be summarized by visit and timing with respect to drug dose. In addition, QTc_F changes from pre-dose will be summarized for number of patients with a change exceeding a threshold of 30 msec or 60 msec.

Other ECG parameters will be reported and summarized. Hart rate (HR) will be summarized as for number of patients ≤ 50 bpm and ≥ 120 bpm, PR interval for number of patients with PR ≥ 220 msec, and duration of QRS complex for number of patients with QRS ≥ 120 msec. RR intervals, when missing, will be calculated from HR using the formula: RR = 60000/HR (in milliseconds, assuming HR in beats per minute). Then QT interval corrected using Fridericia’s formula will be calculated as $\text{QTc}_F = \text{QT}/(\text{RR}/1000)^{1/3}$ (i.e, QT interval in msec divided by cube root of RR interval in seconds).

In all these summaries, QT, PR, QRS durations, and HR will be averaged for ECG taken in triplicate.

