## 2.2. Overall Risk/Benefit Assessment

The risk-benefit relationship has been carefully considered in the planning of this trial. Based on preclinical and clinical data available to date, the conduct of the trial is considered safe and reasonable using the dose and schedule of AGEN2034 as specified for Phase 1, Cohort 1 in this clinical trial protocol.

A Safety Monitoring Committee (SMC) in Phase 1 and an Independent Data Monitoring Committee (IDMC) in Phase 2 are planned for ongoing assessment of the risk-benefit ratio. The trial shall be discontinued in the event of any new findings that indicate a relevant deterioration of the risk-benefit relationship and would render continuation of the trial unjustifiable. The risks of exposure to AGEN2034 include:

- Infusion-related reactions.
- Increase in immune-related adverse events (irAEs), which constitute a unique spectrum of AEs that occur via activation of the subject's immune system and that can sometimes lead to serious and even fatal events ([Boutros et al 2016](#); [Kumar et al 2017](#); [Weber et al 2012](#)).

Infusion-related reactions are a risk inherent to administration of any recombinant protein to humans. The incidence of immunogenicity and the character or severity of immunogenicity-induced side effects cannot be predicted by animal models because humanized or fully human proteins usually provoke a much stronger immune-response in rodents or non-human primates

than in humans. However, for AGEN2034, clinical signs of hypersensitivity were not observed in pilot 4-week IV repeat-dose toxicity studies conducted in cynomolgus monkeys (a primate species closer to human). There were also no findings in an in vitro cytokine release assay in human whole blood.

Immune-related AEs are events that are drug-related and can be explained by an immune phenomenon after other etiologies have been ruled out. Relevant clinical safety experience has been generated with several PD-1 pathway-blocking monoclonal antibodies and with the combination with CTLA-4 agents (Ott et al 2017; Boutros et al 2016; Kumar et al 2017).

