Subjects receiving AGEN2034 should be monitored for infusion reactions. This includes the measurement of vital signs for at least 1 hour after infusion. Subjects will remain in the clinic under close supervision for the duration of this monitoring period. Subjects with mild or moderate infusion reactions may receive AGEN2034 with close monitoring. Premedication with an antipyretic or antihistamine for subsequent treatment administration may be considered. For severe infusion reactions, AGEN2034 infusion must be discontinued, and appropriate medical therapy should be administered.

Subjects who do not experience any infusion related toxicity Grade 1 or higher during or after the infusion may be released from monitoring after one hour if they are otherwise stable.

Subjects with any infusion related toxicity must be managed as per the guidelines in [Table 3](#) and monitoring will continue until any infusion related toxicity has abated to less than Grade 1 and at least one hour has passed from the completion of the entire infusion and flush. All subjects will be given information on and instructions regarding both infusion related toxicity, which is expected to be most likely in the hour after completion of the infusion, and immune related AEs, before leaving the study site. This will include instructions on when and how to return for immune mediated toxicities associated with PD-1 blockade.

Once the AGEN2034 infusion rate has been decreased by 50% or interrupted due to an infusion-related reaction, it must remain decreased for all subsequent infusions. If the subject has a second infusion-related reaction that is Grade  $\geq 2$  on the slower infusion rate, infusion should be stopped and the subject should discontinue treatment. If a subject experiences a Grade 3 or Grade 4 infusion-related reaction at any time, the subject must discontinue treatment. If an infusion reaction occurs, all details about drug preparation and infusion must be recorded.

Should infusion reaction be considered a significant safety issue by the SMC, the SMC might decide to recommend premedication with an antihistamine and acetaminophen approximately 30 to 60 minutes before each dose of AGEN2034 (e.g., 25-50 mg diphenhydramine, 500-650 mg paracetamol IV or oral equivalent acetaminophen). This regimen may be modified based on local treatment standards and guidelines, as appropriate.

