Full serum chemistry 	X								X	X	X			
Hematology tests 	X		X	X			X	X	X	X	X			
Coagulation tests 	X			X			X		X	X	X			
Endocrine function tests 	X			X			X		X	X	X			
Urinalysis 	X			X			X		X	X	X			
Serum pregnancy test	X 													
Urine pregnancy test		X 					X		X	X	X			
Study drug administration 														
AGEN2034			X		X		X	X						

Abbreviations: ADA: anti-drug antibody; AEs: Adverse Events; d: day; ECG: electrocardiogram; ECOG: Eastern Cooperative Oncology Group; IERC: Independent Endpoint Review Committee; m: month; PBMC: peripheral blood mononuclear cell; PGx: pharmacogenomics; PK: pharmacokinetics; w: week.

Note: Where applicable, assessments performed prior to treatment unless otherwise indicated.

 All subjects who discontinue treatment will have at least one Follow-up Visit at 3 months (± 7 days) after last dose of study drug. Subjects who discontinue due to disease progression and/or start of a new line of therapy will then end participation in the trial. Subjects who received the maximum administrations of the combination of AGEN2034; who have achieved a complete response (CR) according to RECIST 1.1; or who have discontinued treatment due to reasons other than disease progression and/or start of a new line of therapy will be in Follow-up for up to approximately 12 months after last dose of study drug or until disease progression and/or start of a new line of therapy. Every effort should be made to collect subject information on the start of new antineoplastic therapy, disease progression and death.

 After the first Follow-up Visit, subjects that present(ed) with progressive disease and/or start new line of therapy will move into Survival Follow-up and should be contacted by telephone every 2 months for up to 12 months after last dose of study drug to assess for survival status. Post-study treatments and the subject's response to them will also be collected.

 Treatment administration and associated procedures for that visit may be delayed for treatment related AEs beyond the window and subsequent schedule adjusted accordingly.

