### **6.4.3.3. Vital Signs, Height and Weight**

Vital signs, height, and weight will be measured and recorded as specified in [Section 6.1](#) (Phase 1, [Table 11](#) or [Table 12](#)) or [Section 6.2](#) (Phase 2, [Table 13](#)). The investigator or qualified designee will take vital signs at the specified times including prior to the administration of each dose of trial treatment. Vital signs include temperature, pulse, respiratory rate, and blood pressure. Weight should be measured prior to dosing. Height will be measured at Visit 1 only.

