5. DEFINITIONS AND CONVENTIONS FOR DATA HANDLING

5.1. DEFINITION OF BASELINE

For all evaluations, unless otherwise noted, baseline is defined as the most recent non-missing measurement prior to the first administration of study drug.

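### SAP 7.6.5 averages vital signs across the whole visit, so any post-infusion readings stored under a dosing visit would be merged with the pre-dose value and acute changes blunted in that table

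*SAP*

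**What the plan says.** SAP 7.6.5 covers body weight and vital signs together. It states: "The observed value and percentage of changes from baseline will be summarized and listed by visit for Safety Analysis Set". It then adds: "If there are multiple measurements per visit, these measurements will be averaged". The only categories defined in the section are for weight loss. Temperature, blood pressure and pulse have no split by time relative to dose, no worst-value summary and no threshold count.

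The protocol places readings on both sides of the infusion:

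- Section 6.4.3.3, before dosing: "The investigator or qualified designee will take vital signs at the specified times including prior to the administration of each dose of trial treatment".
- Section 5.4.3, on monitoring for infusion reactions: "This includes the measurement of vital signs for at least 1 hour after infusion". It gives no number of readings and no instruction on data entry.
- The general note to Table 13 sets a default: "Where applicable, assessments performed prior to treatment unless otherwise indicated". The vital-signs row of that table carries no footnote adding post-infusion times.

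Under SAP 5.1, "baseline is defined as the most recent non-missing measurement prior to the first administration of study drug". When vital signs are taken before the first infusion on Cycle 1 Day 1, as Table 13 schedules, that reading is the baseline.

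**The concern.** Protocol 2.2 puts infusion reactions first among the risks of exposure: "Infusion-related reactions are a risk inherent to administration of any recombinant protein". Hypotension, tachycardia and drug fever are among the signs listed in section 5.4.3. The vital-sign quantity that bears on this risk is the change within a dosing visit, from before the infusion to after it. A rule that averages over the visit removes part of that change. On Cycle 1 Day 1 it also averages the baseline into the value that is compared with baseline.

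The table matters because protocol 8.3.4 names changes in vital signs as part of the safety assessment, alongside adverse events. In addition, protocol 7.1.2 keeps abnormal investigational findings out of AE reporting unless they come with symptoms, lead to discontinuation or are judged medically important. On a natural reading this includes vital signs, although the section does not name them. A post-infusion change that no investigator labels as an event might then appear only in the vital-sign data.

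**Working it through.** The plan states no figure on this point, so there is nothing to reproduce. The check compares the SAP's own rules and then works through the arithmetic of the average.

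**How the SAP treats similar data**

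| Data | Rule | Where |
|---|---|---|
| Weight in the exposure analysis | Repeat values averaged only within a timepoint | SAP 7.6.1 |
| Laboratory values | Shift from baseline to worst post-baseline value, scheduled or not | SAP 7.6.4 |
| ECG | Abnormality and QTcF counts "will be summarized by visit and timing with respect to drug dose"; QTcF change from pre-dose; triplicates averaged | SAP 7.6.6 |
| Vital signs | All values in a visit averaged; no timing split, no worst value | SAP 7.6.5 |

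SAP 5.5 does not resolve the matter. It keeps data from unscheduled visits out of the by-visit tables, but a post-infusion reading at a scheduled dosing visit does not belong to an unscheduled visit.

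**Arithmetic**

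Inputs: one pre-dose reading P; m post-infusion readings, of which j are at an abnormal level A and the rest equal P. The values of P, A, m and j are assumptions, because the documents give none.

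Visit mean = [P + jA + (m - j)P] / (m + 1) = P + [j / (m + 1)] x (A - P).

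The share of the acute change that survives is therefore j / (m + 1).

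| m | j | Share kept | Systolic 120 to 80 mmHg | Temperature 37.0 to 39.0 C | Pulse 80 to 130 bpm |
|---|---|---|---|---|---|
| 1 | 1 | 1/2 = 50% | 100 | 38.0 | 105 |
| 2 | 1 | 1/3 = 33% | 106.7 | 37.67 | 96.7 |
| 4 | 1 | 1/5 = 20% | 112 | 37.4 | 90 |
| 4 | 4 | 4/5 = 80% | 88 | 38.6 | 120 |

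Take systolic pressure on Cycle 1 Day 1, where baseline is P = 120. The true change is (80 - 120)/120 = -33.3%. The reported change would be:

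- m = 1, j = 1: (100 - 120)/120 = -16.7%
- m = 4, j = 1: (112 - 120)/120 = -6.7%
- m = 4, j = 4: (88 - 120)/120 = -26.7%

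Some of the change is always lost, because the pre-dose value is always in the average. The loss is largest when one brief abnormal reading sits among several normal ones. It is smallest when the abnormality persists through all the post-infusion readings.

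**The case against.** The strongest reply is that the blending is not shown to happen. Table 13 defaults assessments to before treatment and lists no post-infusion vital-sign times. The hour of readings in protocol 5.4.3 is a bedside monitoring instruction. The averaging sentence is generic, also covers weight, and fits simple repeat readings. ECGs are split by timing in SAP 7.6.6 because Table 13 schedules them before and after infusion. All of this stands, and it makes the point conditional. A reader might infer from the SAP's mention of multiple measurements that post-infusion values are in the database; the text does not establish that.

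A second reply also stands. A reader might infer that the trial's infusion-reaction signal is itself diluted. The documents do not support that:

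- Protocol 7.1.8 makes an infusion reaction of any grade an event of special interest with expedited reporting.
- SAP 7.6.2 tabulates infusion-related events from investigator reports, by grade.
- SAP 7.6.1 counts doses with reactions, and interrupted doses, from the exposure data.

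None of these passes through the vital-sign average. Fever or hypotension reported as an AE would also appear in the general TEAE tables. Tachycardia has partial cover: SAP 7.6.6 counts subjects with an ECG heart rate of 120 bpm or more, and Table 13 schedules ECGs 2 hours after the first infusion and 1 hour after infusion at later indicated cycles. Blood pressure and temperature have no such second source outside AE reporting.

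Nor should it be inferred that the vital-sign table would look flat. In the cases above, 20% to 80% of the change remains.

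What the replies leave untouched is the wording. The rule averages per visit, and if both kinds of reading are captured it merges them.

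**Conclusion.** The point holds in a narrow form. As written, SAP 7.6.5 would merge pre-dose and post-infusion vital signs at a dosing visit and so understate acute changes in blood pressure, temperature and pulse in the by-visit summary. With one reading on each side, half of the change remains; with one abnormal reading among four post-infusion readings, 20% remains. These sizes use illustrative values and assume that post-infusion readings are entered in the eCRF under the same visit, which the documents leave open. If only the pre-dose reading is captured, nothing is blended and the baseline issue on Cycle 1 Day 1 disappears. It is also unclear whether the by-visit listing would show individual or averaged values.

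The effect is confined to the vital-sign summary. Infusion-reaction counts and grades, the primary endpoint and the sample size are unaffected. This is a minor point of secondary safety reporting, worth correcting because the SAP already handles weight and ECG more carefully.

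**What to change.** In SAP 7.6.5:

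1. Restrict averaging to replicates taken at the same timepoint, as SAP 7.6.1 does for weight.
2. Where post-infusion vital signs are recorded, summarise them separately from pre-dose values by timing relative to dose, as SAP 7.6.6 does for ECG.
3. For those data, report each subject's worst post-infusion change from that day's pre-dose value for blood pressure, pulse and temperature.
4. State that the listing shows individual readings with their timing.

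The sponsor should first confirm whether post-infusion readings and their times are in the database. If they are, the cost is SAP wording and one extra descriptive table. If they are not, only items 1 and 4 apply and the cost is a sentence or two. No clinical procedure or management rule changes.

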7.6.7. Pregnancy tests

Dates and results of pregnancy tests will be listed within Safety Analysis Set.

7.7. EFFICACY ANALYSIS

7.7.1. Best Overall Response and Objective Response per RECIST 1.1

Best overall response (BOR) will be derived from time-point RECIST 1.1 assessments, either by IERC or by investigator. For the primary endpoint, tumor responses will be evaluated using IERC assessments. In the primary analysis, BOR will be evaluated over all on-study time-point assessments recorded before start of a new anti-cancer therapy, in consideration of RECIST 1.1 definition: “The best overall response is the best response recorded from the start of the study treatment until the end of treatment taking into account any requirement for confirmation. On occasion a response may not be documented until after the end of therapy so protocols should be clear if post-treatment assessments are to be considered in determination of best overall response” (Eisenhauer *et al 2009*). Since all assessments are considered for BOR, the confirmed objective response or stable disease (SD) may occur after a transient time-point progressive disease (PD) assessment(s).

In the secondary analysis, conducted for sensitivity evaluation, an alternative, more conservative approach will be used, evaluating BOR only over time-point assessments until first observed PD, as initially proposed in RECIST 1.0 (Therasse *et al 2000*). Such a definition was implemented in the Charter of IERC, therefore BOR evaluation derived by IERC will be used as sensitivity analysis.

Confirmation of objective response (complete response [CR] or partial response [PR]) is required for respective BOR of CR or PR. Confirmation must be obtained at a subsequent assessment at least 4 weeks apart. In case of CR, the confirmatory assessment must be performed at a consecutive assessment, except for intercurrent non-evaluable assessments.

In case of PR, confirmatory assessment after initial CR/PR may be obtained a) in the primary analysis any time at least 4 weeks apart from the initial assessment, without restrictions on intercurrent assessment b) in the IERC-derived BOR evaluation, any time after 4 weeks and after at most 1 intercurrent assessment of non-evaluable (NE) or SD.

For patients who did not fulfill requirements for BOR of CR or PR as described above, BOR of SD is defined, in the primary analysis, as i) initial time point assessment(s) of SD, PR, CR without PD at a minimum interval of 39 days (6 weeks-3 days), disregarding NE assessments and/or ii) unconfirmed PR or CR any time at initial evaluation, without PD at a minimum interval of 39 days and/or iii) durable SD following transient PD: at least 2 assessment(s) of SD, PR, CR (ignoring intercurrent NE assessments) at least 39 days (6 weeks-3 days) apart and without new PD within 84 days, counting time from the last transient PD assessment. Subjects who have a response of PR or CR with no subsequent tumor assessments will be assigned a BOR of SD and will be flagged in listings. In the sensitivity analysis performed using IERC-derived BOR evaluation of SD is only considered based on only criterion i) above.

For patients with time point assessment(s) of PD, excluding any transient PDs (PD followed by confirmed objective response or durable SD) and who do not satisfy criteria for BOR of CR, PR, and SD described above, the BOR assessments in the primary analysis will be PD. In the

sensitivity analysis, using IERC-derived BOR evaluation, a similar definition will be used but without excluding transient PDs.

Finally, BOR of NE will be assigned where there are either no evaluable time point assessments at all or first time point assessment(s) of SD was before minimum interval of 39 days without evaluable assessments preformed after 39 days.

The objective response rate (ORR) is the percentage of subjects with a BOR of PR or CR (i.e., objective response). The primary analysis of ORR will include only confirmed responses, with sensitivity analyses based on unconfirmed responses, derived from timepoint assessments according to RECIST 1.1 guidance for studies not requiring confirmation of response (i.e., occurrence of time-point assessment of CR or PR anytime on study). Subjects with missing tumor response status assessment will be counted as non-response (that is, subjects without any follow-up assessment) will be counted in the denominator for ORR.

BOR determined by investigator and by IERC will be compared by cross-tabulating categories of both BOR evaluations in a 2-way table.

BOR and ORR will be listed for Safety Analysis Set as available using primary and alternative definitions. For confirmed response, duration of response will be listed (see Section 7.7.3). The listings of time-point response will include assessments of target lesion, non-target lesions, and new lesion data, as well as percentage change from baseline in the sum of diameters of target lesions.

7.7.2. Time to Response

Time from treatment initiation to start of objective response (in days) will be summarized using descriptive statistics in subjects with confirmed CR or PR.

7.7.3. Duration of Response

Duration of response (DOR) will be analyzed only for subjects who responded to the study treatment. DOR is defined as the time from first observation of CR or PR which was subsequently confirmed until the first time of disease progression or death by any cause within 12 weeks of last tumor assessment. All assessments performed before initiation of a new anti-cancer therapy will be considered for evaluation of DOR. Similar to evaluation of BOR, in the primary analysis any transient time-point PD(s) will be disregarded for determination of DOR when followed by confirmed objective response or durable stable disease, as defined in section 7.1.1. In the alternative (sensitivity) analysis, DOR will be counted using the date of first observed PD, whether transient or not.

The starting event for DOR will be the date of first objective response. The terminating event will be date of PD or death within 12 weeks of last tumor assessment, whichever occurs first. The censoring event will be the earliest of the dates of last evaluable assessment, last evaluable assessment performed before initiation of new anti-cancer therapy (if applicable), or before 2 or more missed imaging assessments (i.e., no assessment within 90 days) followed by PD or death.

DOE will be reported in months and summarized by quartiles estimated from Kaplan-Meier curve, as well as Kaplan-Meier estimates at 6, 9, 12, 18 months. Number and percent of censored and non-censored observations and a plot Kaplan-Meier curve will be provided.

In addition, duration of observation of DOE (whether censored or not) will be summarized as “Observed DOE”, including the shortest and longest observation will be provided with censoring indicator.

